[REDACTED]	19

2.11	Interim analysis.....	20
3	Sample size calculation	20
3.1	Primary endpoint	20
3.2	Secondary endpoints.....	20
4	Change to protocol specified analyses	21
5	Appendix	21
5.1	Imputation rules	21
5.1.1	AE date imputation	21
5.1.2	Concomitant medication date imputation	22
5.2	Statistical models	24
5.2.1	Rule of exclusion criteria of analysis sets	24
6	Reference	24

List of tables

Table 1-1	Objectives and related endpoints	7
Table 2-1	Pharmacokinetic parameters from Non-compartmental analysis	13
Table 2-2	Clinically notable laboratory values.....	16
Table 3-1	Sensitivity of confidence interval precision to change in assumption for GCV rate	20

List of figures

Figure 1-1	Study design	6
------------	--------------------	---

List of abbreviations

AE	Adverse Event
AKI	Acute Kidney Injury
AUC	Area Under Curve
BMI	Body Mass Index
CSR	Clinical Study Report
CV	Coefficient of Variation
eGFR	Estimated Glomerular Filtration Rate
EOS	End of Study
FAS	Full Analysis Set
FIH	First In Human
GCV	Geometric Coefficient of Variation
HV	Health Volunteers
IA	Interim Analyses
ICF	Informed Consent Form
IV	Intravenous
KDIGO	Kidney Disease Improving Global Outcomes
LLOQ	Lower Limit of Quantification
LOCF	Last Observation Carried Forward
████████	████████
MedDRA	Medical Dictionary for Drug Regulatory Affairs
PD	Pharmacodynamic(s)
PK	Pharmacokinetic(s)
PT	Preferred Term
RRT	Renal Replacement Therapy
SA-AKI	Sepsis-Associated Acute Kidney Injury
SAF	Safety set
SAP	Statistical Analysis Plan
SAS	Statistical Analysis System
SCR	Screening set
SMQ	Standardized MedDRA Query
SOC	System Organ Class
SOFA	Sequential Organ Failure Assessment
ULOQ	Upper Limit of Quantification

1 Introduction

The purpose of the document is to describe the statistical analyses to be included in the clinical study report (CSR) to be produced at the time the last patient has completed the study CTIN816B12201. The document covers the safety analysis and the efficacy analysis on the data in the study.

[figure not shown]
1.1 Study design

This is a multicenter, participant and investigator-blinded, randomized, placebo-controlled study to characterize PK/PD profile and to evaluate the safety and the efficacy of TIN816 in hospitalized adult participants with diagnosis of sepsis and acute kidney injury (AKI). Approximately 20 participants will be randomized in the study. The study consists of a screening period (up to 48 hours), treatment period (Day 1), and post-treatment period (Day 2 to 90) and is summarized in [Figure 1-1](#).

An interim analysis (IA) is planned when approximately 8 participants complete Day 14 visit. The study will continue without modification if a similar PK profile of TIN816 compared to the one in the healthy volunteers (HV) is confirmed. Otherwise, an adaptive design would be implemented with options to add up to two additional arms testing a higher dose, multiple bolus doses, extended infusion dosing regimens or combination of bolus dose and extended infusion.

The adaptive design will be supported by modeling and simulation with data from the preclinical studies, first in human (FIH) study and the IA of the current PK/PD study. Patient recruitment will continue during the IA to enroll up to a cap of 12 patients. In the circumstance that the first IA does not provide sufficient PK data to support phase 2b, an additional IA will be added when all 20 patients complete Day 14 visit.

Figure 1-1 Study design

^A interim analysis (IA) based on 8 patients with 14-day data collected from baseline

^B conditional additional interim analysis (IA) based on 20 patients with 14-day data collected from baseline

* participant-investigator blinded

1.2 Study objectives and endpoints

Table 1-1 Objectives and related endpoints

Objective(s)	Endpoint(s)
Primary objective(s) 
• To assess pharmacokinetics (PK) of TIN816 with a single dose of IV infusion	Endpoint(s) for primary objective(s) 
• TIN816 concentrations in serum PK parameters: C_{max}, T_{max}, $T_{1/2}$, Cl, V_z, AUC_{last} and AUC_{inf} of TIN816
Secondary objective(s) 
• To assess safety and tolerability of TIN816 vs placebo	Endpoint(s) for secondary objective(s) 
• Safety evaluations (including adverse events/serious adverse events, safety laboratory parameters, vital signs and immunogenicity)

1.2.1 Primary estimands

The estimand is the precise description of the treatment effect and reflects strategies to address events occurring during study conduct which could impact the interpretation of the study results (eg. premature discontinuation of treatment).

The primary clinical question of interest is: What are the pharmacokinetic characteristics (systemic exposure) of TIN816 (IV infusion) in hospitalized adult participants with diagnosis of SA-AKI, who received the complete treatment infusion?

The primary estimand is described by the following attributes:

1. Population: hospitalized adult patients with diagnosis of SA-AKI with complete IV infusion and at least one available valid PK concentration measurement who survived at Day 7.
2. Primary endpoint: PK parameters, including C_{max} , T_{max} , $T_{1/2}$, Cl , V_z , AUC_{last} and AUC_{inf} .
3. Treatment of interest: A single dose of investigational study treatment TIN816 will be administered via an IV infusion.

4. Handling the intercurrent events: PK will be evaluated in patients who remain alive until Day 7.
5. The summary measure: geometric mean and median.

1.2.2 Secondary estimands

As the intention of estimand framework is applied to efficacy endpoints, considering all safety outcomes are the secondary endpoint, the estimand framework for secondary estimands is not further discussed.

Estimand considerations in case of COVID-19 pandemic impact

The overarching principle for primary and secondary estimands is answering questions of interest regarding the treatment effect of TIN816 that are valid in conditions when the COVID-19 pandemic is no longer present.

It is not known whether TIN816 (recombinant CD39) can influence the clinical course of an infection with coronavirus SARS-CoV-2 (COVID-19). TIN816 is designed to treat acute organ injuries. Data capture and clinical evaluation activities include possible adaptations to restrictions for participant access to investigational sites in case of a new infection wave. Additional supplementary analysis as well as sensitivity analyses may be performed due to the presence of a considerable amount of deviations from the normal methods of participant follow up and data capture or other pandemic-related intercurrent events.

2 Statistical methods

2.1 Data analysis general information

Data will be analyzed according to Section 9 of the CTIN816B12201 Clinical Trial Protocol. The most recent version of the SAS® and R software available in the statistical programming environment will be used for the analysis.

In general, categorical data will be presented as frequencies and percentages in descriptive statistics. For continuous data, mean, standard deviation, median, minimum and maximum will be presented. For selected parameters, 25th and 75th percentiles will also be presented.

For PK parameters, n, mean, median, minimum, maximum, coefficient of variation (CV (%)) to mean, geometric mean, and CV (%) to geometric mean will be presented.

2.1.1 General definitions

The term “**study treatment**” and/or “**study drug**” refers to the 2-hour study infusion drug during the study, that is TIN816 2 mg/kg.

For analysis purposes, “**Baseline**” is defined to be the last result obtained at or prior to start of study treatment (Day 1) for baseline demographics, medical history, lab values, vital signs and ECGs. Most variables will have their baseline at Day 1, unless otherwise specified. For assessments not performed at Day 1, the assessment at the screening visit or most recent assessment prior to start of study treatment will be used as baseline.

The reference creatinine baseline is defined as below.

For hospital-acquired AKI, a stable serum creatinine obtained in the hospital prior to AKI should be used as reference baseline, otherwise, baseline serum creatinine in the following order of preference:

1. Median value within 3 months of the hospital admission. If not available:
2. Median value between 3 and 6 months prior to hospital admission. If not available:
3. At hospital admission.

“Post-Baseline” is defined for analysis purposes to be any value collected after the “baseline” as defined above for analysis purposes.

The term **“study day”** is defined relative to the analysis reference date, which is the date of first administration of study treatment.

The *study day* for a scheduled or unscheduled visit on or after the analysis reference date is defined as:

Study day = (Date of Visit) – (analysis reference date) +1.

The *study day* for a scheduled or unscheduled visit before the analysis reference date is defined as:

Study day = (Date of visit) – (analysis reference date).

Thus the analysis reference date (date of first administration of study treatment) will be study day 1 and the date directly prior the analysis reference date will be study day □1 (there is no study day 0).

The term **“unscheduled visit”** refers to visits that occurred not as part of the Clinical Trial Protocol assessment schedule. Data collected at unscheduled visits will, in general, not be used in ‘by-visit tabulations’ or graphs, but they will be included in analyses of safety parameters based on all post-baseline values such as summary statistics of clinically notable abnormalities of laboratory data. For efficacy evaluations, measurements from unscheduled visits will generally not be used, unless where otherwise specified. All data collected at both scheduled and unscheduled visits will be included in data listings.

“Completion”: a participant will be considered to have completed the study when the patient has completed the Day 90 visit in the study or End of Study (EOS) for participants who discontinue from the study. The maximum of the date of last visit in the randomized treatment period, date of withdrawal of consent (in case of withdrawal from study), would be the date of **last contact** for the patient in the study.

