1.3 Schedule of activities (SoA)

The SoA lists all of the assessments when they are performed. All data obtained from these assessments must be supported in the participant's source documentation. The "X" in the table denotes the assessments to be recorded in the clinical database or received electronically from a vendor. The "S" in the table denotes the assessments that are only in the participant's source documentation and do not need to be recorded in the clinical database.

Participants should be seen for all visits/assessments as outlined in the SoA or as close to the designated day/time as possible. Missed or rescheduled visits should not lead to automatic discontinuation. Unscheduled visits may occur at any time for adverse event/serious adverse event follow-up and/or to repeat any laboratory assessment due to safety and/or technical reasons.

Participants who discontinue from the study should be scheduled for a final evaluation visit if they agree, as soon as possible, at which time all of the assessments listed for the final visit will be performed. At this final visit, the adverse events and concomitant medications not previously reported must be recorded on the electronic case report forms (eCRF).

As per [Section 4.5](#), during a public health emergency as declared by local or regional authorities i.e. pandemic, epidemic or natural disaster that limits or prevents on-site study visits, alternative methods of providing continuing care may be implemented by the investigator as the situation dictates. If allowable by a local health authority, national and local regulations and depending on operational capabilities, phone calls, virtual contacts (e.g. tele consultation) or visits by site staff/ off-site healthcare professional(s) staff to the participant's home, can replace certain

protocol assessments, for the duration of the disruption until it is safe for the participant to visit the site again. If the investigator delegates tasks to an off-site healthcare professional, the investigator must ensure the individual(s) is/are qualified and appropriately trained to perform assigned duties. The investigator must oversee their conduct and remain responsible for the evaluation of the data collected.

Table 1-2 Assessment Schedule

Period	Screening	Treatment			Post-treatment Visits									
Visit Name	Screening	Day 1 ²			Day 2	Day 3	Day 5	Day 8	Day 11	Day 14	Day 21	Day 30	Day 60	Day 90/End of Study (EOS)

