A total of approximately 20 participants will be randomized for the study. After informed consent is obtained from the participant/legal representative and the participants' eligibility is confirmed, study sites will perform the screening and baseline (Day 1) assessments following the assessment schedule (Table 1-2). Participants will be randomly assigned to receive either TIN816 at 2 mg/kg or placebo using a 3:1 allocation ratio (TIN816:placebo). A single dose of the study treatment will be administered via 2-hour IV at the randomization visit in a participant and investigator-blinded fashion. The study treatment must be administered within 48 hours, after SA-AKI is first diagnosed, but ideally as soon as possible. Two PK samples will be taken at Day 1, one prior to study treatment and one immediately after the completion of IV infusion (within 15 minutes), and additional samples will be taken at Day 2, 3, 5, 8, 14, 30, 60 and 90, optimally always at the same time of the day as when dosing of TIN816 started on Day 1. All participants will be followed-up for a total duration of 90 days.

An interim analysis is planned when approximately 8 participants complete Day 14 visit. The study will continue without modification if a similar PK profile of TIN816 compared to that in the HV is confirmed. Otherwise, an adaptive design would be implemented with options to add up to two additional arms testing a higher dose, multiple bolus doses, extended infusion dosing regimens or combination of bolus dose and extended infusion. The adaptive design will be supported by modeling and simulation with data from the preclinical studies, FIH study and the interim analysis of the current PK/PD study. Patient recruitment will continue during the IA to enroll up to a cap of 12 patients. In the circumstance that the first IA does not provide sufficient PK data to support phase 2b, an additional IA will be added when all 20 patients complete Day 14 visit.

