7.5 Early study termination by the Sponsor

The study can be terminated by Novartis at any time.

Reasons for early termination include (but are not limited to):

- Unexpected, significant, or unacceptable safety risk to participants enrolled in the study
- Decision based on recommendations from applicable board(s) after review of safety and efficacy data
- Discontinuation of study treatment development

In taking the decision to terminate, Novartis will always consider participant welfare and safety. Should early termination be necessary, participants must be seen as soon as possible and treated as a participant who discontinued from the study. The participant should come in for a final End of Study (EOS) visit. The investigator may be informed of additional procedures to be followed in order to ensure that adequate consideration is given to the protection of the participant's interests. The investigator or Novartis depending on local regulation will be responsible for informing Institutional Review Boards (IRB)/Independent Ethics Committees (IEC) of the early termination of the study.

8 Study Assessments and Procedures

Study procedures and their timing are summarized in [Section 1.3](#) Schedule of Activities. Protocol waivers or exemptions are not allowed.

Adherence to the study design requirements, including those specified in [Section 1.3](#) Schedule of Activities, is essential and required for study conduct.

Repeat or unscheduled samples may be taken for safety reasons or for technical issues with the samples.

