2.3.1 Patient disposition

The number of patients screened, screened but not enrolled, completed and discontinued from the study will be summarized. The reasons for screen failure will be provided for the FAS by treatment group. Patients discontinued from the study will also be summarized with reasons for discontinuation. If the disposition is related to COVID-19, the relationship to COVID-19 will also be presented.

The number of subjects with protocol deviations will be tabulated by deviation category as well as deviation related to COVID-19 for the FAS. The number of patients by country will also be presented.

Demographic and baseline characteristics table include but not limited to the following information:

- Informed consent provider (Self/Legal guardian)
- Age
- Sex
- Ethnicity
- Race
- Weight [kg]
- Height [cm]
- Body mass index (BMI) [kg/m²]
- Smoking history
- Alcohol history
- Baseline serum creatinine value (as defined above in [Section 2.1.1](#))

Sepsis diagnosis characteristics at screening visit and APACHE II score at Day 1 include the following information:

- SOFA score ≥ 2 (yes/no)
- Septic shock (yes/no)
- Presumptive source of the infection
- Blood culture performed (yes/no)
 - Positive: Gram positive bacteria, Gram negative bacteria, fungal infection, other
 - Negative
- APACHE II score

AKI diagnosis at screening visit include but not limited to following information:

- Diagnosis of AKI based on KDIGO Serum Creatinine criteria (yes/no)
- Stage of AKI stage based on DKIGO criteria
- Serum creatinine level
- Urine output
- Fluid resuscitation (yes/no)
- Vasopressor (yes/no)
- Renal replacement therapy (yes/no)
- Mechanical ventilation (yes/no)

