2.5.1 Primary endpoint(s)/Primary estimand(s)

The primary endpoint is all TIN816 concentrations in serum PK parameters, including C_{max} , T_{max} , $T_{1/2}$, Cl , V_z , AUC_{last} and AUC_{inf} , and other relevant PK parameters (data permitting) (Table 2-1). It will be summarized descriptively for participants with at least one dose of study treatment.

There is no inferential analysis to be performed.

TIN816 serum concentration data will be listed by treatment, participant and visit/sampling time point. Descriptive summary statistics of TIN816 serum concentration data will be provided by treatment, and visit/sampling time point, including the frequency of concentrations below the LLOQ and reported as zero.

Summary statistics will include mean (arithmetic and geometric), standard deviation (SD), CV (arithmetic and geometric), median, minimum and maximum. An exception to this is T_{max} where median, minimum, and maximum will be presented. PK data will also be represented graphically (including spaghetti plots, and mean plots with SD) by treatment arm, participant and visit. Overlaying individual serum concentration-time profiles will be generated by treatment arm participant and visit/sampling time point.

Drug concentrations below LLOQ will be treated as missing for the calculation of the geometric means and geometric CV%, and as zero for all other calculations including calculation of PK parameters. Pharmacokinetic parameters will be calculated as described in CTIN816B12201 Protocol and will be listed by treatment and participant and summarized by treatment with descriptive statistics as listed below.

The pharmacokinetic parameters listed in the table below will be determined from the serum concentration time data using the actual recorded sampling times and non-compartmental method(s) with Phoenix WinNonlin (Version 6.4 or higher). Other relevant PK parameters may be added (data permitting).

Table 2-1 Pharmacokinetic parameters from Non-compartmental analysis

PK parameter	Definition
AUC_{last}	The area under the curve (AUC) from time zero to the last measurable concentration sampling time (T_{last}) (mass \times time \times volume-1)
AUC_{inf}	The AUC from time zero extrapolated to infinity (mass \times time \times volume-1)
AUC_{inf} / D	The AUC from time zero to infinity (mass \times time \times volume-1), normalized by actual dose (mg/kg)
AUC_{0-14d}	The AUC from time zero to 14 days post-dose (mass \times time \times volume-1)

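### The SAP counts an early final visit as study completion, so a discontinuer can be both completed and discontinued, and no rule keeps that visit's data out of the Day 90 summaries

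*SAP*

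**What the plan says.** - **Completion.** SAP 2.1.1 counts a participant as complete when they have "completed the Day 90 visit in the study or End of Study (EOS) for participants who discontinue from the study".
- **Discontinuation.** Protocol 7.2 defines it as permanently stopping further required assessments or follow-up, for any reason.
- **Disposition table.** SAP 2.3.1: "The number of patients screened, screened but not enrolled, completed and discontinued from the study will be summarized". It adds the reasons for discontinuation.
- **Final evaluation of discontinuers.** Protocol 1.3 asks for a visit as soon as possible, if the participant agrees, "at which time all of the assessments listed for the final visit will be performed". In Table 1-2 the final visit is one column, visit 200, that serves as both Day 90 and End of Study.
- **EOS used for an early visit.** On early termination by the sponsor, Protocol 7.5 says: "The participant should come in for a final End of Study (EOS) visit".
- **What is measured at Day 90.** For PK, Protocol 4.1 says "additional samples will be taken at Day 2, 3, 5, 8, 14, 30, 60 and 90". Protocol 8.4 adds hematology, chemistry, urinalysis, coagulation, anti-drug antibodies (ADA) and vital signs.
- **By-visit summaries.** SAP 2.5.1: "Descriptive summary statistics of TIN816 serum concentration data will be provided by treatment, and visit/sampling time point". SAP 2.6.1 does the same for laboratory data and vital signs.
- **Exclusion from by-visit tables.** SAP 2.1.1 generally leaves out unscheduled visits; the term "refers to visits that occurred not as part of the Clinical Trial Protocol assessment schedule".

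**The concern.** Completed and discontinued are normally exclusive outcomes. Here the completion rule names discontinuers and admits them, so the two rows can overlap and no longer add up to the number randomized.

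The second issue is where the early evaluation's data go. It is prescribed in Protocol 1.3 and has no column of its own. If it is entered under the shared Day 90/EOS column, acute-phase values will sit beside true 90-day values. With about 15 participants on TIN816, one such record can dominate a descriptive row. For serum concentration, a late row that should be near zero could show a sizeable mean.

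**Working it through.** The plan states no figure on this point and gives no discontinuation rate, so there is nothing to reproduce. The first part compares the rules; the other two are illustrations on stated assumptions.

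**1. Do the categories overlap?** Take a participant who leaves on Day 10 and attends the final evaluation.

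- Protocol 7.2: discontinued, because further required follow-up has stopped.
- SAP 2.1.1: completed, through the clause for participants who discontinue.
- SAP 2.3.1: counted in both rows. No visible rule gives one status precedence.

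**2. Size in the disposition table.** Input: about 20 randomized (SAP 1.1). Assume d participants discontinue and attend the early evaluation, and all others reach Day 90. Completed is 20/20 under the SAP wording and (20 − d)/20 under a Day-90-only rule. The two SAP rows sum to 20 + d.

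| d | Completed, SAP wording | Completed, Day 90 only | Completed + discontinued, SAP wording |
|---|---|---|---|
| 1 | 100% | 95% | 21 |
| 2 | 100% | 90% | 22 |
| 3 | 100% | 85% | 23 |
| 5 | 100% | 75% | 25 |

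**3. Size in the Day 90 concentration row, if an early sample is filed there.** Inputs from the documents:

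- 15 participants on TIN816 (SAP 3.1).
- LLOQ of about 10 ng/mL (Protocol 8.7).
- Values below the LLOQ are missing for the geometric mean and zero for other statistics (SAP 2.5.1).

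Assumptions that the documents do not supply:

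- All 15 contribute to the row, and the other 14 are below the LLOQ at Day 90.
- Concentration reaches 10 ng/mL at Day 38. This borrows the minimum monitoring period after overdose in Protocol 6.7, which is not a measured time to LLOQ at the study dose.
- Decline is mono-exponential with a half-life of 4 to 8 days.

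Formula: C(Day 10) = 10 × 2^((38 − 10)/half-life). The arithmetic mean is C/15, the geometric mean is C (n = 1), and the median is 0.

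| Half-life | C at Day 10 (ng/mL) | Geometric mean | Arithmetic mean | Median |
|---|---|---|---|---|
| 4 days | 10 × 2^7 = 1,280 | 1,280 | 85 | 0 |
| 6 days | 10 × 2^4.67 = 254 | 254 | 17 | 0 |
| 8 days | 10 × 2^3.5 = 113 | 113 | 7.5 | 0 |

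Without the early sample the arithmetic mean would be 0 and no geometric mean could be calculated. The pattern holds for any early value: the geometric mean equals it, the arithmetic mean is one fifteenth of it, and the median does not move.

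**4. What does not change.** Cmax, Tmax, the AUCs, half-life, clearance and volume are derived from actual recorded sampling times (SAP 2.5.1), so the visit label has no bearing on them.

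**The case against.** **Discontinuers are not hidden.** A reader might infer that they are reported as completers instead of as discontinuers. SAP 2.3.1 does not support that: it reports them as discontinued, with reasons. The completion sentence also stands next to the definition of last contact and may have been meant to mark when follow-up ends. This limits the harm, but the sentence defines completion and the overlap follows from it.

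**The Day 90 mapping is not written down.** A reader might infer that Day 10 data will be tabulated as Day 90. No section says so. A Table 1-2 footnote says visit numbers are for internal programming only, and SAP 2.1.1 derives study day from the visit date. An early evaluation could be classed as unscheduled and kept out of by-visit tables. This stands: the mapping is possible, not stated. But the exclusion does not clearly cover the visit. Protocol 1.3 prescribes it, and describes unscheduled visits as adverse-event follow-up or repeat laboratory tests. The visible SAP does not use study day to assign visits.

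**The primary analysis is largely untouched.** The primary estimand concerns PK parameters, which do not change, and no inference is planned. SAP 2.5.1 also reports the frequency of values below the LLOQ, the median, the range, listings and individual profiles, so one high value among 14 below the LLOQ would be noticeable. All of this stands. The exposure is limited to Day 90 descriptive rows and plots.

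**Few participants can trigger it.** Treatment is a single infusion, and those who stop it stay in follow-up (Protocol 7.1). Those who die or decline the visit provide no early sample. This also stands.

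**Conclusion.** The completion definition is wrong as written. A discontinuer who attends the early evaluation is both completed and discontinued, and the completed count is overstated by 1 of about 20 for each. This follows from the text and needs no assumption beyond such a participant existing.

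The visit-assignment point is a gap. Early PK, laboratory and vital-sign data can enter the Day 90 rows and plots because the documents neither direct them there nor keep them out. The concentration figures (geometric mean 113 to 1,280 ng/mL, arithmetic mean 7.5 to 85 ng/mL) show how one record could dominate a row. They rest on an assumed half-life and Day 38 anchor and are not estimates of what will occur.

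Two further inferences are not supported. The first is that creatinine clearance summaries would be contaminated: the SAP sections that may cover them are not visible. The second is that the completion rate feeds phase 2b planning: the Protocol refers only generally to operational insights (4.2).

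**What to change.** 1. In SAP 2.1.1, define completion as attending the Day 90 visit only, so that completed and discontinued are mutually exclusive. The last-contact definition can stay, so the date imputation in SAP 5.1 is unaffected.
2. Give the early-discontinuation evaluation its own visit label, separate from Day 90.
3. State that in by-visit tables and plots its data are assigned to the scheduled visit matching the actual study day, or are only listed. If assigned, say which record is used when two fall at the same visit.
4. Keep these data in worst-value, adverse-event and ADA analyses, and leave the non-compartmental analysis as it is.

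The cost is about two sentences in the SAP and one label in the database. The one downside is that the reported completion rate becomes less favourable.
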